- To describe the risk of severe IS as effectiveness outcome patients with NVAF (overall population as well as patients with renal impairment) initiating treatment with individual NOACs (rivaroxaban, apixaban, edoxaban) compared to phenprocoumon
- To describe the treatment persistence in patients with NVAF (overall population as well as patients with renal impairment) initiating treatment with individual NOACs (rivaroxaban, apixaban, edoxaban) compared to phenprocoumon

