9.3 Variables

9.3.1 Exposure definition

As exposure, we will assess prescriptions of phenprocoumon and NOACs, i.e. rivaroxaban (15 mg or 20 mg once daily), apixaban (2.5 mg or 5 mg twice daily), edoxaban (30 mg or 60 mg once daily). All prescriptions will be assessed based on the documented dispensation date. A detailed list of products with the corresponding central pharmaceutical number (CPN) of the study drugs is displayed in Annex 3: Additional information.

Each patient will be assigned to one of the four exposure groups based on the index drug: new users of phenprocoumon, rivaroxaban, apixaban or edoxaban.

Exposure time for phenprocoumon and NOACs starts on the index date and will be calculated as the sum of days of supply + a grace period of 14 days (in case of treatment discontinuation). A gap period of 30 days between the estimated end of supply and any following prescription of the index drug is allowed.

Since NOACs are prescribed in a fixed dose, the days of supply corresponds to the number of tablets in a dispensed package for rivaroxaban and edoxaban (used once daily) or half the number of tablets in a package for apixaban (used twice daily).

As of an international normalized ratio (INR) between 2 and 3, phenprocoumon patients are often asked to titrate or change their daily doses. Therefore, the exposure time calculation for phenprocoumon is not straightforward . In an anonymous empirical data collection using phenprocoumon diaries of anticoagulated NVAF patients in the university medical center of Schleswig-Holstein information on phenprocoumon dosing will be collected. The results of this survey will be used to calculate a median daily dose which will then be used as the basis for the phenprocoumon exposure time in this study.

As a sensitivity analysis, to account for the intra- and interpersonal variability of phenprocoumon treatment, a personalized defined daily dose (pDDD) based on the observed phenprocoumon prescriptions for each patient in the InGef database will be calculated. For this purpose, amount of active ingredient (AAI) dispensed to each patient of the phenprocoumon group will be obtained for each prescription. A prescribed personalized daily dose (pPDD) representing the average daily dose taken during follow-up will be computed for each patient i such that:

$$pPDD_{i} = \frac{\sum_{k=1}^{K-1} AAI_{i,k}}{T_{i}}$$

- $k = \text{index of the prescriptions received during follow-up } (k \in \{1, K\}).$

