- T= number of days between the first and the last prescription during follow-up

For the sake of simplicity, only prescriptions of patients who were solely treated with phenprocoumon during follow-up will be included in the computation of the empirical DDD (eDDD). Patients with a pDDD below the 5th or above the 95th percentile and patients with only one prescription for phenprocoumon will be assigned the median pDDD (=eDDD) over all patients.

The exposure time (ET) corrected from the intra- and interpersonal variability of phenprocoumon treatments can be computed for each patient i as:

$$ET_i = \frac{\sum_{k=1}^{K} AAI_{i,k}}{pDDD}$$

Patients will be considered as having discontinued treatment with the index drug, if they did not receive a subsequent prescription of the respective drug between the last prescription and a gap period of 30 days.

Patients will be considered as having switched from the index drug to phenprocoumon or another NOAC if they received a prescription of the respective drug during continuous exposure time to the index drug as described above. The date of the first prescription of phenprocoumon or another

NOAC will be defined as the date of treatment switch at which patients will be censored. For the comparison of the effectiveness outcomes in patients receiving reduced vs. standard doses of NOACs (other objectives), patients will also be censored if they switch from reduced to standard dose or vice versa.

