9.7.2 Main analysis

Analyses will be conducted in line with good statistical practices. Models will use confounding factors to adjust for group differences. However, unmeasured confounding and resulting confounding bias affecting point estimates, confidence intervals and any p-values in the treatment group comparisons may remain.

In a first step, Cox proportional hazards regression models will be applied in in each treatment group compared to phenprocoumon (reference) to estimate crude and confounder adjusted hazard ratios (HRs) of the above mentioned outcomes as well as treatment discontinuation (persistence) with accompanying 95% confidence intervals and *p*-values. Persistence (risk of non-persistence) will also be calculated separately for specific time points of interest (months 3, 6, 9, 12, 18 and 24). In the analysis of reduced vs. standard dose of NOACs, the standard dose will be used as reference. Kaplan-Meier cumulative incidence plots will be generated to characterize risk of outcome events of interest over time.

Information on confounding factors which are planned to be included in the models as well as in the estimation of the propensity score can be found in section 9.3.3.

In a second step, we will use the stabilized inverse probability of treatment weighting (IPTW) approach based on the propensity score to adjust for potential confounding resulting from imbalances in the baseline characteristics of different treatment groups. The objective of IPTW

based analysis is to create a weighted sample, for which the distribution of possible confounding variables is approximately the same between comparison groups (12,13). The propensity score is defined as the patient's probability to receive a treatment under investigation (i.e. phenprocoumon for main analyses and standard dose for the analyses of reduced vs. standard dose of NOACs) given a set of known patient's baseline characteristics. Propensity scores will be calculated using multiple logistic regression on a relevant set of patient characteristics listed in section 9.3.1 for each 1:1 comparison separately, e.g. rivaroxaban vs. phenprocoumon, rivaroxaban 15 mg vs. rivaroxaban 20 mg etc.

Let Z be an indicator variable relating to the treatment received by a patient, Z = 1 for an active treatment (e.g. rivaroxaban), Z = 0 for a control treatment (warfarin), and let X denote a vector of observed patient baseline characteristics. Then the propensity score is e = P(Z = 1|X). The inverse

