9.7.3 Sensitivity analysis

We will conduct three pre-defined sensitivity analyses to prove the consistency of our results. First, we will repeat the Cox regression analysis for IS/ SE as combined endpoint and ICH (primary objectives) as well as for the analysis of treatment discontinuation allowing for stockpiling of phenprocoumon and NOACs, i.e. if a prescription of the index drug is refilled before the estimated end of supply, the remaining supply of the prescription will be added to following prescription. Second, we will perform the Cox regression analysis for the outcomes ICH, IS, SE, severe IS, kidney failure, AKI and fatal bleeding excluding patients with a prior outcome event in the baseline period, i.e. major bleeding for ICH and fatal bleeding, IS or SE for IS and severe IS, SE (see covariate definition in Annex 3: Additional information). Third, we will repeat the Cox regression analysis for IS/ SE as combined endpoint and ICH analyses using the pDDD to calculate the supply for phenprocoumon as defined in section 9.3.1.

No actions will be taken to deal with missing data, since data from all dimensions is assumed to be complete.

All analysis will be performed using SAS Enterprise guide version 7.1 or R.

The statistical concept of the study described above will be supplemented by the more detailed statistical analysis plan.

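### One median daily dose for every phenprocoumon user, combined with a 30-day gap, biases the persistence comparison, and the planned personalised-dose sensitivity analysis leaves persistence out

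*Protocol*

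**What the plan says.** **Exposure (Protocol 9.3.1).** NOAC days of supply are the number of tablets in the pack, or half that number for apixaban. For phenprocoumon the protocol notes that "phenprocoumon patients are often asked to titrate or change their daily doses". It then plans a diary survey at one university centre, whose results are "used to calculate a median daily dose which will then be used as the basis for the phenprocoumon exposure time". The value is not yet known, and one figure is applied to all phenprocoumon users.

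**Discontinuation (9.3.1).** One rule serves all drugs: "A gap period of 30 days between the estimated end of supply and any following prescription of the index drug is allowed". Later in the same section a patient counts as having discontinued "if they did not receive a subsequent prescription of the respective drug between the last prescription and a gap period of 30 days". The former sentence starts the gap at the estimated end of supply. The latter appears to start it at the last prescription.

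**Persistence (8.2, 9.7.2).** A secondary objective reads "To describe the treatment persistence in patients with NVAF", for each NOAC compared with phenprocoumon. It is analysed by Cox model, with a hazard ratio, confidence interval and p-value, and also at six time points from month 3 to month 24.

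**Sensitivity analyses (9.7.3).** There are three. The first, stockpiling, covers IS/SE, ICH and treatment discontinuation. The second excludes patients with prior events. The third is the only one that changes the phenprocoumon dose: "Third, we will repeat the Cox regression analysis for IS/ SE as combined endpoint and ICH analyses using the pDDD". Treatment discontinuation is not in it.

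**The concern.** Of all the endpoints, persistence is the one computed most directly from the assumed daily dose. For IS/SE and ICH the dose acts only through the censoring date. For persistence it sets the event itself.

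The error is one-sided. A patient below the median dose makes a pack last longer than the computed supply. Once the refill is more than 30 days late, an adherent patient is recorded as having stopped. A patient above the median refills early and is correctly kept as persistent, so the two do not cancel. No NOAC user is misclassified through this particular route.

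Stockpiling does not test this. It carries forward supply left over from early refills, and a patient who refills late because of a low dose has none to carry.

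The protocol introduces the pDDD for exactly this variability within and between patients, but does not apply it to the endpoint most exposed to it. At stake is a reported persistence advantage for NOACs that comes partly or wholly from how phenprocoumon supply was calculated.

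**Working it through.** **1. Reproduce the protocol's own figures.** Section 7, Figure 1, ischaemic stroke rows. Rate per 100 person-years = events / (n × mean days / 365.25) × 100.

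- Phenprocoumon, one tablet per day: 201 / (9,871 × 219.56 / 365.25) × 100 = 3.39 (stated 3.39)
- Phenprocoumon, empirical daily dose: 276 / (9,871 × 415.4 / 365.25) × 100 = 2.46 (stated 2.46)
- Rivaroxaban 15 mg: 90 / (2,786 × 347.27 / 365.25) × 100 = 3.40 (stated 3.40 and 3.4)

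The follow-up figures are internally consistent.

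**2. Effect of the dose rule in that table.** The 9,871 phenprocoumon patients are the same under both rules.

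| | One tablet/day | Empirical dose | Change | Rivaroxaban |
|---|---|---|---|---|
| Mean days | 219.56 | 415.4 | × 1.89 | 347.27 |
| Median days | 148 | 308 | × 2.08 | 238.5 |
| Ratio to rivaroxaban, mean | 0.63 | 1.20 | | |
| Ratio to rivaroxaban, median | 0.62 | 1.29 | | |

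Phenprocoumon follow-up moves from shorter than rivaroxaban to longer when only the dose rule changes.

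**3. When an adherent patient is labelled as stopped.** Let the pack hold N tablets, the imposed dose be m and the true dose d, both in tablets per day. The refill is more than 30 days late when N/d − N/m > 30, that is, when d/m < 1 / (1 + 30m/N). Assume that d is lognormal with median exactly m, so that σ = √ln(1 + CV²), which is 0.198 for CV 20% and 0.472 for CV 50%. The share affected at the first pack is Φ(ln(threshold)/σ). N, m and CV are assumptions; the protocol gives none of them.

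| N | m | Threshold d/m | Share, CV 20% to 50% |
|---|---|---|---|
| 100 | 0.5 | 0.870 | 24% to 38% |
| 100 | 0.75 | 0.816 | 15% to 33% |
| 100 | 1.0 | 0.769 | 9% to 29% |
| 50 | 0.5 | 0.769 | 9% to 29% |
| 50 | 1.0 | 0.625 | 1% to 16% |

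The range is about 1% to 38%.

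**4. Effect on the hazard ratio when true persistence is identical.** Illustrative simulation; all inputs except the gap and grace periods are assumed: 5,000 per arm, two years, 30-day gap from end of supply, 14-day grace, 98-tablet packs, true phenprocoumon median 0.7 tablets/day, refill timing SD 10 days, true stopping rate 0.4 per year in both arms. HR is NOAC versus phenprocoumon, and below 1 favours NOACs.

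- Imposed median correct (0.7), between-patient log-SD 0 / 0.25 / 0.35 / 0.5: HR 1.00 / 0.69 / 0.63 / 0.60.
- Log-SD 0.25, imposed dose 0.4 / 0.5 / 0.6 / 0.7 / 0.8 / 1.0: HR 1.32 / 1.16 / 0.93 / 0.69 / 0.53 / 0.32.

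A correct median does not remove the bias, and a wrong one can move the HR across 1.

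**5. Candidate checks on the same inputs** (one variant had 50-tablet phenprocoumon packs). One dose for everyone at the survey's 25th percentile, median and 75th percentile gave HRs of roughly 0.84 to 0.95, 0.59 to 0.72 and 0.40 to 0.53. All three point the same way although the true HR is 1. The pDDD gave about 0.98 to 1.11.

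**6. Why the pDDD is a bound and not the truth.** From the two formulas in 9.3.1, pDDD = (AAI₁ + … + AAI_{K−1}) / T and ET = (AAI₁ + … + AAI_K) / pDDD. Substituting gives ET = T + AAI_K / pDDD. Total supply therefore reaches the last prescription by construction, which tends to overstate phenprocoumon persistence.

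**The case against.** The median will be measured from patient diaries, not guessed. Persistence is one of many descriptive secondary objectives, and the Abstract says that p-values and confidence intervals must not be read as confirmatory. The primary outcomes already have the dose sensitivity analysis. NOAC supply is itself imputed at one or two tablets a day, and section 9.9 acknowledges exposure misclassification in general. All of this stands and limits the weight of the point. It does not remove it: step 4 shows that a correct median still leaves a bias, and non-confirmatory labelling does not correct a shift in one direction. Section 9.9 expects little misclassification under continuous dispensing, yet this error falls on patients who are dispensed continuously.

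Three stronger readings are tempting, and the protocol does not support them.

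- *The 1.89-fold contrast is the size of the bias here.* It is follow-up to an outcome event, in a renal-impairment subgroup on rivaroxaban 15 mg, in an earlier study whose gap and grace rules are not given. Neither dose rule is this study's main rule.
- *A particular percentage of adherent users will be misclassified.* Pack size, dose and spread all come from outside the document, and 50-tablet packs give much lower figures than 100-tablet packs.
- *Agreement of runs at the survey's 25th percentile, median and 75th percentile would settle the direction.* Each run still imposes one dose on everyone, so together they can endorse the artefact (step 5).

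**Conclusion.** The point holds for persistence versus phenprocoumon. One dose for all phenprocoumon users with a 30-day gap biases the hazard ratio towards NOACs when doses vary between patients and the imposed median is about right. An imposed median well below the true one could push it the other way. No planned sensitivity analysis of discontinuation varies the dose.

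The size in this study cannot be fixed, because neither the survey dose nor its spread is given. Figure 1 shows only that the choice of dose rule can reverse the order of follow-up. Under the assumed inputs, a true HR of 1 appears as about 0.6 to 0.7. The direction of these illustrations matters more than the values.

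The calculations start the gap at the estimated end of supply. If it literally started at the last prescription, a patient using up a 98-tablet once-daily pack would already count as stopped, so the two statements must be reconciled. This is a worthwhile, low-cost improvement to a secondary analysis. It is not a flaw in the primary comparison.

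**What to change.** In section 9.7.3, extend the third (pDDD) sensitivity analysis to treatment discontinuation, for both the hazard ratio and the month 3 to 24 estimates. Report it beside the main result and describe it as an opposite bound, for the reason in step 6.

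State that no direction of persistence versus phenprocoumon will be concluded if the median-dose and pDDD results differ in direction.

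Runs at the survey's 25th and 75th percentile doses may be added to show a range. Say explicitly that their agreement does not license a directional claim.

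In section 9.3.1, reconcile the two statements of where the 30-day gap begins.

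Cost: one extra run of a model already programmed, using a dose variable already planned. The downside is that the persistence result may have to be given as a range.

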9.2.3 Exclusion criteria

Patients meeting any of the following exclusion criteria (see Annex 3: Additional information) will be excluded from the analysis:

• A verified ambulatory or primary/ secondary hospital discharge diagnosis of valvular atrial fibrillation in the baseline period;

- A verified ambulatory or primary/ secondary hospital discharge diagnosis indicating pregnancy in the baseline period;
- A verified ambulatory or primary/ secondary hospital discharge diagnosis of a transient cause of atrial fibrillation in the baseline period;
- A verified ambulatory or primary/ secondary hospital discharge diagnosis of venous thromboembolism (VTE) in the previous or same quarter of the index date;
- A claim for hip or knee replacement surgery in the 60 days prior to or on the index date;
- A prescription of heparin or fondaparinux in the 60 days prior to or on the index date;
- A prescription of more than one oral anticoagulant (rivaroxaban, apixaban, edoxaban or phenprocoumon) on the index date;
- A prescription of warfarin or dabigatran in the baseline period or on the index date;
- A verified ambulatory or primary/ secondary hospital discharge diagnosis of end-stage kidney disease or a claim for dialysis in the baseline period;
- Patients receiving an initial dose of rivaroxaban 10 mg/ 2.5 mg or edoxaban 15 mg (these dosages are not indicated for the treatment of NVAF).
- A prescription of contraindicated drug for apixaban or rivaroxaban due to drug interactions (i.e. azole antifungals and HIV protease inhibitors) in the 60 days before or on the index date.

For the main analysis, patients will be followed from the index date until the first diagnosis of the respective outcome event, discontinuation of the index drug, death, end of continuous insurance in the SHI or the end of the study period (31 December 2017), whichever comes first. Patients will be censored in all analyses if they switch to phenprocoumon or another NOAC (including dabigatran), receive a prescription of heparin/ fondaparinux, warfarin, rivaroxaban 10 mg/ 2.5 mg, edoxaban 15mg or a contraindicated drug as defined above. For specific analyses, the end of follow-up may differ as described in 9.3.1.

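### The personalised phenprocoumon dose is measured inside a follow-up that the single-median supply rule may already have ended, so steady low doses mostly cannot be measured

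*Protocol*

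**What the plan says.** Section 9.3.1 of the protocol bases phenprocoumon days of supply in the main analysis on one median daily dose, to be taken from a diary survey at a single university centre. A gap of up to 30 days after the estimated end of supply is tolerated.

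The same section sets up a sensitivity analysis with a personalised dose (written both pPDD and pDDD; I treat them as one quantity), "representing the average daily dose taken during follow-up". It is the amount of active ingredient summed over all prescriptions but the last, divided by T. The prescriptions are indexed by k, the "index of the prescriptions received during follow-up", and T is the "number of days between the first and the last prescription during follow-up". Patients outside the 5th to 95th percentiles get the median (eDDD) instead, and "patients with only one prescription for phenprocoumon will be assigned the median pDDD (=eDDD) over all patients".

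Follow-up is defined in 9.2.3: for the main analysis, patients are followed "until the first diagnosis of the respective outcome event, discontinuation of the index drug, death", or until insurance or the study period ends. That section adds: "For specific analyses, the end of follow-up may differ as described in 9.3.1". Section 9.3.1 gives no other end of follow-up for the personalised dose. The only variation it describes is censoring at a dose switch in the comparison of reduced with standard NOAC dose.

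Section 9.7.3 uses the personalised dose to recalculate phenprocoumon supply for IS/SE and ICH, as one of three analyses meant to show that results are consistent.

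**The concern.** The personalised dose exists to capture how phenprocoumon dosing varies within and between patients. A single median works worst for patients on clearly lower doses: their packs outlast the assumed supply, so they are classed as discontinued and censored while still treated. A sensitivity analysis on dosing should be able to correct exactly these patients.

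If the personalised dose uses only prescriptions inside a follow-up that the median-dose rule has already closed, the refill that would reveal a low dose falls outside the window. The patient then counts as having one prescription and is given the eDDD. At stake is whether this analysis can test the main IS/SE and ICH results for low-dose users of the comparator.

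**Working it through.** **Inputs from the protocol.** The 30-day gap after end of supply, supply based on one survey median m, the formula for the personalised dose, its window and the fallback (all 9.3.1); the end of follow-up (9.2.3). Most phenprocoumon products listed in Annex 3 with a strength are 3 mg. The 14-day grace period does not matter here, because a refill within 30 days already continues exposure.

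**Inputs assumed, because the protocol does not give them.** m = 1.5 to 3.0 mg/day; packs of 20, 50 or 98 tablets of 3 mg (60, 150 or 294 mg); adherent patients with a lognormal daily dose and between-patient CV of 30% to 50%; and, for the table only, a true database median equal to m.

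**The floor.** A refill stays in follow-up only if its interval is at most AAI/m + 30. Summed over the K - 1 intervals, T is at most ΣAAI/m + 30(K - 1). Hence every measurable dose is at least m/(1 + 30m/A), where A is the mean amount per prescription. With a constant pack P this equals P/(P/m + 30). A steady user below it has K = 1. Such a floor exists for any m and any pack; only its height depends on the assumptions.

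Example: P = 294, m = 2.25, CV 40%.
- Longest tolerated interval: 294/2.25 + 30 = 160.7 days. Floor: 294/160.7 = 1.83 mg/day, or 81% of m.
- σ = √ln(1 + 0.4²) = 0.385. Share below: s = Φ(ln(0.813)/0.385) = 29.6%.
- Median of the remaining distribution relative to the true median: exp(σ·Φ⁻¹(s + (1 - s)/2)) = 1.16.

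| Pack (mg) | m (mg/day) | Floor (mg/day) | Floor/m | Share below, CV 30/40/50% | eDDD/true median |
|---|---|---|---|---|---|
| 294 | 1.5 | 1.30 | 87% | 31.4 / 35.6 / 38.2% | 1.13-1.27 |
| 294 | 2.25 | 1.83 | 81% | 24.1 / 29.6 / 33.1% | 1.09-1.22 |
| 294 | 3.0 | 2.30 | 77% | 18.1 / 24.4 / 28.6% | 1.07-1.19 |
| 150 | 1.5 | 1.15 | 77% | 18.6 / 24.8 / 28.9% | 1.07-1.19 |
| 150 | 3.0 | 1.88 | 63% | 5.5 / 11.1 / 16.0% | 1.02-1.10 |
| 60 | 1.5 | 0.86 | 57% | 2.8 / 7.3 / 11.8% | 1.01-1.07 |
| 60 | 3.0 | 1.20 | 40% | 0.1 / 0.9 / 2.6% | 1.00-1.02 |

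**Simulation with irregular refills** (m = true median = 2 mg, log-SD 0.35, 10% noise in refill intervals, 5th/95th percentile rule applied):

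| | 300 mg packs | 150 mg packs |
|---|---|---|
| Floor = smallest dose obtained | 1.67 mg | 1.43 mg |
| All patients with K = 1 | 31% | 18% |
| Below floor: K = 1 | 89% | 86% |
| Below floor: given the eDDD | 94% | 96% |
| Below floor with K > 1: measured/true dose | 1.13 | 1.13 |
| eDDD (true median 2.00) | 2.30 mg | 2.15 mg |

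**The protocol's Figure 1 (section 7).** The phenprocoumon stroke rates reproduce: 201/(9871 × 219.56/365.25) = 3.39 and 276/(9871 × 415.4/365.25) = 2.46 per 100 person-years. Changing from one tablet per day to an empirical DDD lengthened mean follow-up by 415.4/219.56 = 1.89 times and moved the stroke HR from 0.84 to 1.02.

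**A second wording of discontinuation.** Later in 9.3.1 the 30 days appear to run from the last prescription rather than from the estimated end of supply. Taken literally, the floor would be P/30: 60/30 = 2.0, 150/30 = 5.0 and 294/30 = 9.8 mg/day. The working above uses the end-of-supply wording.

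**The case against.** The best reply is that the premise is one reading. The 9.2.3 rule is introduced for the main analysis, and the protocol nowhere says outright that the survey-median rule closes the dose window. Section 9.3.1 also limits the eDDD to patients treated only with phenprocoumon during follow-up. That restriction does little inside a follow-up already censored at any switch, so a wider window may have been meant. This stands as a doubt about intent. But 9.2.3 sends the reader to 9.3.1 for exceptions, and 9.3.1 states none for this dose. If a wider window was intended, the text must say so.

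Four stronger conclusions that a reader might draw are not supported:
- *Low-dose patients simply get the main-analysis median back, so agreement is built in.* The main analysis uses the survey median; the fallback is the database eDDD. If the true database median were 25% below m (an assumption), then with 150 mg packs and m = 3.0 the eDDD would be 2.49-2.79 mg and supply 8-21% longer than in the main analysis (3.0/2.79 = 1.08; 3.0/2.49 = 1.21). With 294 mg packs, across m = 1.5 to 3.0, it would run from 12% shorter to 8% longer. The direction is open.
- *Low doses are never observed.* In the simulation 11-14% of patients below the floor have a second prescription and are measured, though too high.
- *Figure 1 gives the size of the bias.* It compares one tablet per day with an empirical DDD, and neither is this protocol's main rule. It shows only that results are sensitive to the phenprocoumon exposure definition.
- *Between 18% and 38% of patients are affected.* That is the largest-pack case. The document gives no pack sizes.

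The reach is also limited: one of three sensitivity analyses, Cox models only, in a study whose p-values are declared non-confirmatory. Leaving it to the analysis plan is not a full answer, because the protocol itself fixes the formula, the window and the fallback.

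**Conclusion.** The point holds on the protocol as written. Formula, window, discontinuation rule and fallback together leave steady doses below P/(P/m + 30) generally unmeasured. They also push the eDDD above the true database median. The sensitivity analysis for IS/SE and ICH therefore cannot properly correct early censoring of low-dose phenprocoumon users. Whether their supply ends up shorter or longer than in the main analysis depends on how the survey median compares with the database eDDD.

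The mechanism is algebra; the size is illustrative. Under the assumptions listed, 0-12% of adherent patients fall below the floor with 20-tablet packs, about 6-29% with 50-tablet packs and 18-38% with 98-tablet packs. In the last case the eDDD is 7-27% too high. It is worth correcting before the analysis is run, but it does not touch the main analysis.

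**What to change.** In 9.3.1, define the window for the personalised dose and T independently of the median-dose discontinuation rule: all phenprocoumon dispensings from the index date to the first of switch, disenrolment, death or 31 December 2017. Then rebuild supply with the resulting dose and the same 30-day gap rule, and keep the eDDD only for patients with a single dispensing in that window. In the simulation, changing the window alone cut K = 1 from 31% to 1% (300 mg packs) and from 18% to 0% (150 mg packs), and the eDDD returned to 2.00 mg. The share of patients below the floor given the eDDD fell from 94% to 19% and from 96% to 29%. Nearly all of that remainder comes from the percentile replacement, which the simulation retained; if the study keeps it too, report how many patients it affects.

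Separately, reconcile the two descriptions of discontinuation in 9.3.1 (30 days from the last prescription, or from the estimated end of supply).

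The cost is a few sentences and modest reprogramming of one sensitivity analysis on data already held. The downside is that true interruptions would count as low dosing and add unexposed time to phenprocoumon. Using each patient's median of amount dispensed over refill interval limits this, but only with three or more dispensings; with two, the single interval sets the dose.
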